10.10.8. Substudy B Intervention and Concomitant Therapy

10.10.8.1. Study Intervention(s) Administered

Study interventions for Substudy B will include:

10.10.8.1.1. Group 1: Combination RSVpreF + qIRV 1.0-mL Formulation

GROUP 1	Vaccine Details				
COMBINATION 1.0 mL (RSVpreF + qIRV)	Vaccine Component	RSVpreF	qIRV		
		2 Stabilized RSV prefusion F antigens, in equal amounts from virus subgroups A and B	Encoding HA of 4 strains as recommended for the influenza season (2 A strains and 2 B strains)		
	Dose Formulation	RSV vaccine 120 µg/vial powder for solution for injection	Quadrivalent influenza suspension for injection, COI mg/mL (qIRV)		
	Product for Reconstitution	Sterile water as diluent for injection (0.65 mL/syringe)	N/A		
	Unit Dose Strength(s)	120 µg	μg		
	Route of Administration	After combining both vaccines, a single 1-mL IM injection is given into the deltoid muscle of the nondominant arm (preferred).			
	Use	Experimental			
	IMP or NIMP/AxMP	IMP			
	Sourcing	Provided centrally by Pfizer RSVpreF is supplied as a lyophilized white cake, packaged in a clear glass 2-mL vial with a rubber stopper, aluminum overseal, and flip-off cap. For the 1.0-mL formulation, the white cake is GCI qIRV is supplied as GCI			
	Packaging and Labeling				
		Study intervention(s) will be labeled as per country requirements.			

10.10.8.1.2. Group 2: Combination RSVpreF + qIRV 0.5-mL Formulation

GROUP 2	Vaccine Details		
COMBINATION 0.5 mL	Vaccine	RSVpreF	qIRV
(RSVpreF + qIRV)	Component	2 Stabilized RSV prefusion F antigens, in equal amounts from virus subgroups A and B	Encoding HA of 4 strains as recommended for the influenza season (2 A strains and 2 B strains)
	Dose Formulation	RSV vaccine 120 µg/vial powder for solution for injection	Quadrivalent influenza suspension for injection, mg/mL (qIRV)
	Product for Reconstitution	qIRV suspension	N/A
	Unit Dose Strength(s)	120 µg	μg
	Route of Administration	After combining qIRV suspension with the RSVpreF cake, a single 0.5-mL IM injection is given into the deltoid muscle of the nondominant arm (preferred).	
	Use	Experimental	
	IMP or NIMP/AxMP	IMP	
	Sourcing	Provided centrally by Pfizer	
	Packaging and Labeling	RSVpreF is supplied as a lyophilized white cake, packaged in a clear glass 2-mL vial with a rubber stopper, aluminum overseal, and flip-off cap. For the 0.5-mL formulation, the white cake is to be GCI qIRV is supplied as GCI Study intervention(s) will be labeled as per country requirements.	

10.10.8.1.3. Administration

See Section 6.2.1.

10.10.8.1.4. Medical Devices

See Section 6.2.2.

10.10.8.1.5. Preparation, Handling, Storage, and Accountability

See Section 6.3.

10.10.8.1.5.1. Preparation and Dispensing

See Section 6.3.1.

10.10.8.1.6. Allocation to Study Intervention

See Section 6.4.

Allocation of study intervention in Substudy B will be conducted via the IRT:

 Visit B101: Randomize the participant and then obtain the kit/container number assignment.

10.10.8.2. Blinding

This is an observer-blinded study.

10.10.8.2.1. Blinding of Participants

Participants will be blinded to their assigned study intervention.

10.10.8.2.2. Blinding of Site Personnel

The study staff receiving, storing, dispensing, preparing, and administering the study interventions will be unblinded. All other study and site personnel, including the investigator and investigator staff, will be blinded to assignment of study intervention. In particular, the individuals who evaluate participant safety will be blinded. Because the administered volume and appearance differ between study interventions, study interventions will be administered in a manner that prevents the participants from identifying the study intervention based on these factors.

The PI will assign the responsibility of the unblinded dispensers/administrators to persons who will not participate in the evaluation of any study participant. To ensure adequate coverage, at least 2 unblinded dispensers/administrators will be assigned per site. Members of the study site nursing/medical staff or clinic pharmacy will fulfill these roles. Contact between the unblinded dispensers and study participants should be kept to a minimum. The investigator, study coordinator, and any site staff other than the unblinded dispensers/administrators must not be allowed to know the study intervention assigned to any study participant and must not be allowed to see the study intervention container contents.

In the event of a Quality Assurance audit, the auditor(s) will be allowed access to unblinded study intervention records at the site(s) to verify that randomization/dispensing has been done accurately.

10.10.8.2.3. Blinding of the Sponsor

To facilitate rapid review of data in real time, sponsor staff will be unblinded to study intervention allocation for the participants in Substudy B. However, sponsor staff who routinely have contact with blinded site personnel, and who are not involved in ensuring that protocol requirements for study intervention preparation, handling, allocation, and administration are fulfilled at the site, will also remain blinded. Further, details will be provided in a data blinding plan.

10.10.8.2.4. Breaking the Blind

See Section 6.5.4.

10.10.8.3. Study Intervention Compliance

See Section 6.6.

10.10.8.4. Dose Modification

Not applicable to Substudy B.

10.10.8.5. Continued Access to Study Intervention After the End of the Study

See Section 6.8.

10.10.8.6. Treatment of Overdose

See Section 6.9.

10.10.8.7. Prior and Concomitant Therapy

The following concomitant medications and vaccinations will be recorded in the CRF:

- Licensed influenza vaccine received within the 18 months prior to enrollment.
- Any nonstudy vaccinations received from 28 days prior to study enrollment until the last study visit.

Prohibited medications listed below, if taken, will be recorded in the CRF and include start and stop dates, name of the medication, dose, unit, route, and frequency.

10.10.8.7.1. Prohibited During the Study

Receipt of the following vaccines and medications during the time periods listed below may exclude a participant from the per-protocol analysis from that point onward; however, it is anticipated that the participant would not be withdrawn from the study (Section 7). Medications and vaccinations should not be withheld if required for a participant's medical care.

 Investigational vaccines and investigational drugs are prohibited within 28 days prior to enrollment and thereafter during the course of the study. Final Protocol Amendment 1, 30 May 2023

- Licensed or nonstudy investigational RSV vaccines are prohibited at any time prior to study enrollment and thereafter during the course of the study.
- Nonstudy investigational influenza vaccines are prohibited at any time prior to study enrollment and thereafter during the course of the study.
- Licensed influenza vaccines are prohibited ≤180 days before study intervention administration and thereafter during the course of the study.
- Nonstudy inactivated or recombinant vaccines, licensed COVID-19 vaccines, or COVID-19 vaccines authorized for temporary or emergency use are prohibited within 14 days after study intervention administration.
- Nonstudy live vaccines should not be given within 28 days prior to enrollment and thereafter during the course of the study.
- Chronic systemic treatment with known immunosuppressant medications, or radiotherapy, is prohibited within 60 days prior to enrollment and thereafter during the course of the study.
- Systemic corticosteroids (≥20 mg/day of prednisone or equivalent) for ≥14 days are
 prohibited within 28 days prior to enrollment and thereafter during the course of the
 study.
- Blood/plasma products or immunoglobulins are prohibited within 60 days prior to enrollment and thereafter during the course of the study.
- Prophylactic antipyretics and other pain medication to prevent symptoms associated with study intervention administration are not permitted. However, if a participant is taking a medication for another condition, even if it may have antipyretic or pain-relieving properties, it should not be withheld prior to study vaccination.

10.10.8.7.2. Permitted During the Study

- Medication other than that described as prohibited in Section 10.10.8.7.1 required for the treatment of preexisting conditions or acute illness is permitted.
- Inhaled/nebulized, intra-articular, intrabursal, or topical (eg, skin, eyes, ears) corticosteroids are permitted.

10.10.9. Discontinuation of Substudy B Intervention and Participant Discontinuation/Withdrawal

See Section 7.

10.10.10. Substudy B Assessments and Procedures

10.10.10.1. Immunogenicity Assessments

10.10.10.1.1. Blood Collection

Blood samples (approximately 50 mL per sample) for immunogenicity assessments will be collected from all enrolled participants just prior to study vaccination at Visit B101, and at Visit B102. The total blood sampling volume for individual participants is approximately 100 mL across 1 month.

Instructions for the collection and handling of blood and serum samples will be provided in the laboratory manual. The date and time of each sample will be recorded.

The immunogenicity samples must be processed and shipped as indicated in the instructions provided to the investigator site to maintain sample integrity. Any deviations from the immunogenicity sample handling procedure (eg, sample collection and processing steps, interim storage, or shipping conditions), including any actions taken, must be documented and reported to the sponsor. On a case-by-case basis, the sponsor may make a determination as to whether sample integrity has been compromised.

10.10.10.1.2. RSV Antigen Immunogenicity Testing

Serum samples collected at both visits will be assayed for RSV A and RSV B serum NTs.

RSV A and RSV B serum NTs will be determined and reported as the NT at each blood sampling visit.

Sample collection, processing, storage, and shipping information can be found in the laboratory manual. All assays will be performed by Pfizer and/or at a facility designated by Pfizer.

10.10.10.1.3. qIRV Strain-Specific HAI Testing

Serum samples collected at Visit B101 and Visit B102 will be assayed for seasonal influenza strains (2×A, 2×B) as recommended by WHO for recombinant or cell-based influenza assays.

Immune response testing for seasonal strains (2×A, 2×B) will be assessed by strain-specific HAI antibody titers to evaluate vaccine responses.

Sample collection, processing, storage, and shipping information can be found in the laboratory manual. All assays will be performed by Pfizer and/or at a facility designated by Pfizer.

10.10.10.1.4. Exploratory Assays, Including Immunogenicity Assessments and Assay Development

Samples remaining after completion of the planned assays from blood draws may be used for additional vaccine and infectious disease—related research. Samples may also be used for assay development, standardization, qualification, and validation. This work is critical in the development, qualification, and validation of serological assays and is required by regulatory authorities for their use in the licensure of a vaccine.

10.10.10.2. Biological Samples

See Section 8.2.3.

10.10.10.3. Safety Assessments

See Section 8.3.

10.10.10.4. Adverse Events, Serious Adverse Events, and Other Safety Reporting

See Section 8.4.

10.10.10.5. Stopping Rules

The following stopping rules are in place for Substudy B participants, based on review of AEs, ECG, and laboratory data, and apply to the 28-day period immediately following administration of study vaccination at Visit B101, Day 1 through Day 28. These data will be monitored on an ongoing basis by the investigator (or medically qualified designee) and sponsor in order to promptly identify and flag any event that potentially contributes to a stopping rule. In the event that sponsor personnel confirm that a stopping rule is met, the following actions will commence:

- The IRC will review all appropriate data.
- The stopping rule will PAUSE randomization and any further administration of study vaccination (Visit B101).
- For those participants already vaccinated, all routine study conduct activities, including ongoing data entry, reporting of AEs, participant e-diary completion, blood sample collection, and participant follow-up, will continue during the pause.

10.10.10.5.1. Stopping Rule Criteria

A stopping rule is met if any of the following criteria occur within 28 days after receiving study vaccination (Visit B101).

If any participant vaccinated with RSVpreF + qIRV develops:

 A new ECG abnormality that a cardiologist judges consistent with probable or possible myocarditis or pericarditis, including:

- Sustained atrial or ventricular arrhythmias.
- Second-degree Mobitz Type II or worse AV block or new bundle branch block.
- Diffuse ST-segment elevation or PR-segment inversion, compatible with pericarditis.
- An abnormal troponin I value that is confirmed to be abnormal on repeat testing, assessed as related to study intervention by the investigator.
- If ≥1 participant vaccinated with RSVpreF + qIRV develops confirmed myocarditis or pericarditis.
- If any participant vaccinated with RSVpreF + qIRV dies.
- If ≥1 participant vaccinated with RSVpreF + qIRV experiences a Grade 4 unsolicited AE, or SAE of any severity, assessed as related to study intervention by the investigator.
- 6. If ≥2 participants vaccinated with RSVpreF + qIRV develop the same or similar Grade 3 or higher (see Section 10.3.3, Assessment of Intensity) unsolicited AE (including laboratory abnormalities, except lymphocyte count and C-reactive protein), other than myocarditis/pericarditis, assessed as related to study intervention by the investigator.

Note that the local reactions, systemic events, and fever (Section 8.3.4) reported within 7 days from the day of administration of study vaccination, irrespective of whether they are recorded in the e-diary or as AEs, are excluded from this stopping rule.

A charter for the IRC will be prepared and finalized before the first participant is consented.

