10.9.6. Substudy A Design

10.9.6.1. Overall Design

This study is designed to evaluate the safety, tolerability, and immunogenicity of RSVpreF and a modified RNA vaccine (qIRV) against RSV and influenza when administered as a combined vaccine and when administered alone. This 3-visit study will initially be conducted as a Phase 1b, single-site, parallel-group, randomized, placebo-controlled, observer-blinded substudy.

Approximately 250 healthy participants (n=125 per group) will be enrolled in Substudy A. Note: "Enrolled" means a participant's agreement to participate in a clinical study following completion of the informed consent process.

Healthy adults ≥60 years of age will be randomized 1:1 to either:

- Group 1: combination (RSVpreF + qIRV) (Visit A101) followed by placebo (Visit A102) or
- Group 2: sequential administration of qIRV (Visit A101) followed by RSVpreF (Visit A102) administered 1 month apart.

Randomization will be stratified by 3 age groups (60-64, 65-79, and ≥80 years) within each study site. To ensure a broad representation of age groups (participants at least 65 years of age) for the current recommendation on seasonal influenza vaccination, no more than 40 participants 60 through 64 years of age will be vaccinated.

Blood will be collected prior to each vaccination and at the final study visit.

Local reactions and systemic events occurring within 7 days after each vaccination will be recorded in an e-diary device or smartphone app.

AEs and SAEs will be collected from the signing of informed consent through study completion.

This study will have stopping rules that will apply to participants as specified in Section 8.3.6 with monitoring by designated unblinded sponsor site staff on an ongoing basis. If a stopping rule is confirmed as having been met, further randomization and administration of Vaccination 1 will be paused while additional information is gathered, and cumulative unblinded safety data will be reviewed by the IRC. Participants who have received Vaccination 1 will continue further study visits and procedures as scheduled. A charter for the IRC will be prepared and finalized before the first participant provides informed consent.

The IRC will review cumulative safety data from at least 10 participants who have received RSVpreF + qIRV. Concurrently, enrollment will pause until the IRC confirms a satisfactory safety assessment, whereupon enrollment will recommence.

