10.9.10.5. Stopping Rules

The following stopping rules are in place for Substudy A participants, based on review of AEs, ECG, and laboratory data, and apply to Vaccination 1, Day 1 through Day 28. These data will be monitored on an ongoing basis by the investigator (or medically qualified designee) and sponsor in order to promptly identify and flag any event that potentially contributes to a stopping rule. In the event that sponsor personnel confirm that a stopping rule is met, the following actions will commence:

- The IRC will review all appropriate data.
- The stopping rule will PAUSE randomization and any further administration of Vaccination 1 (RSVpreF + qIRV or qIRV). The PAUSE will not apply to those participants who received Vaccination 1 prior to the stopping rule being met.

 For those participants already vaccinated, all routine study conduct activities, including ongoing data entry, reporting of AEs, participant e-diary completion, blood sample collection, and participant follow-up, will continue during the pause.

A stopping rule is met if any of the following criteria occur within 28 days after receiving Vaccination 1 (RSVpreF + qIRV or qIRV).

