10.9.10.5.1. Stopping Rule Criteria

If any participant vaccinated with qIRV or RSVpreF + qIRV develops:

- A new ECG abnormality that a cardiologist judges consistent with probable or possible myocarditis or pericarditis, including:
 - Sustained atrial or ventricular arrhythmias.
 - Second-degree Mobitz Type II or worse AV block or new bundle branch block.
 - Diffuse ST-segment elevation or PR-segment inversion, compatible with pericarditis.
- An abnormal troponin I value that is confirmed to be abnormal on repeat testing, assessed as related to study intervention by the investigator.
- If ≥1 participant vaccinated with qIRV or RSVpreF + qIRV develops confirmed myocarditis or pericarditis.
- If any participant vaccinated with qIRV or RSVpreF + qIRV dies.
- If ≥1 participant vaccinated with qIRV or RSVpreF + qIRV experiences a Grade 4 unsolicited AE, or SAE of any severity, assessed as related by the investigator.
- 6. If ≥2 participants vaccinated with qIRV or RSVpreF + qIRV develop the same or similar Grade 3 or higher (see Section 10.3.3, Assessment of Intensity) unsolicited AE (including laboratory abnormalities, except lymphocyte count and C-reactive protein), other than myocarditis/pericarditis, assessed as related to study intervention by the investigator.

Note that the local reactions, systemic events, and fever (Section 8.3.4) reported within 7 days from the day of administration of Vaccination 1, irrespective whether they are recorded in the e-diary or as AEs, are excluded from this stopping rule.

A charter for the IRC will be prepared and finalized before the first participant is consented.

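### The note excluding 7-day reactions from the stopping rule does not say which criteria it limits, so a related serious reaction could be read as exempt from the pause

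*Protocol*

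**What the plan says.** Protocol Section 10.10.10.5.1 lists six criteria for Substudy B. The fifth is met when one vaccinated participant "experiences a Grade 4 unsolicited AE, or SAE of any severity, assessed as related to study intervention by the investigator". The sixth needs at least two participants with the same or a similar related unsolicited AE of Grade 3 or higher. A note then says that local reactions, systemic events and fever reported within 7 days of vaccination, "irrespective of whether they are recorded in the e-diary or as AEs, are excluded from this stopping rule". Section 10.9.10.5.1 has the same structure for Substudy A, with the note tied to Vaccination 1: "irrespective whether they are recorded in the e-diary or as AEs, are excluded from this stopping rule".

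The parent sections set out the consequences. Section 10.10.10.5 begins "The following stopping rules are in place for Substudy B participants". It continues: "In the event that sponsor personnel confirm that a stopping rule is met, the following actions will commence". Those actions are review by the internal review committee (IRC) and a pause: "The stopping rule will PAUSE randomization and any further administration of study vaccination". Section 10.9.10.5 provides the same for Vaccination 1 in Substudy A, adding: "The PAUSE will not apply to those participants who received Vaccination 1 prior to the stopping rule being met".

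**The concern.** In the fifth criterion, the word unsolicited qualifies the Grade 4 AE but not the SAE. The note excludes solicited events wherever they are recorded, without saying which criteria it limits and without keeping serious events in. If it covers the whole list, a related solicited reaction that becomes an SAE would be exempt from a criterion that, on its own words, it meets.

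This matters most in Substudy B. Protocol Section 10.10.4.1 says the 0.5-mL mix may affect injection-site reactogenicity, so a serious solicited reaction is an event for which the pause rule should leave no doubt.

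**Working it through.** The check is mainly textual; the plan has no figure to reproduce.

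**1. Can a solicited reaction be an SAE?** Yes, under the protocol's own definitions. Grade 4 includes hospitalization for severe injection-site pain (Section 8.3.4.2, Table 1) and for severe vomiting (Section 8.3.4.3, Table 2). Grade 4 solicited events go on the AE CRF (footnotes to both tables). Inpatient admission is an SAE criterion (Section 10.3.2).

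**2. What does the singular term at the end of the note refer to?** The usage is mixed.
- For the narrow reading: the note directly follows criterion 6; the parent sections open in the plural ("The following stopping rules are in place for Substudy B participants"); and Section 8.4.8 names both AE and SAE where it means both.
- For the broad reading: the list items are called criteria, any one of which meets a stopping rule, and the parent section uses the singular when it states the pause ("The stopping rule will PAUSE randomization and any further administration of study vaccination"). Criterion 6 and the Grade 4 part of the fifth criterion already say unsolicited, so the note adds a new exclusion only where that word is absent, as it is for SAEs.

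**3. Apply both readings to one case:** a related Day 2 admission for injection-site pain.
- Narrow: the fifth criterion is met, and randomization and dosing pause for IRC review once sponsor personnel confirm it.
- Broad: the event is excluded, and neither step is required.

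**4. Would anything else require a study-level pause for this one non-fatal event?**
- Substudy B sentinel hold (Section 10.10.6.1): applies once, and IRC notification depends on an imbalance between groups.
- Substudy A review of at least 10 combination recipients (Section 10.9.6.1): applies once; "enrollment will pause until the IRC confirms a satisfactory safety assessment, whereupon enrollment will recommence".
- Confirmed Grade 4 provision (Sections 8.3.4.2 and 8.3.4.3): requires immediate sponsor notification and, if the event is related, stops further doses for that participant only. Substudy B gives a single dose.
- 24-hour SAE report (Section 8.4.1.1): notification, not a pause.
- IRC monitoring (Section 10.1.5.1) and sponsor discretion (Sections 10.1.9 and 10.10.6.1): allow a pause but do not require one. The IRC's stated minimum duty is review when a stopping rule is met, so it depends on the same wording.

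**5. How does the SAP treat the same overlap?** Sections 3.1.3.3 (Substudy A) and 3.2.1.1 (Substudy B) remove reactogenicity AEs from the AE derivations but retain those that are serious or lead to discontinuation. The protocol's note has no equivalent exception.

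**6. How much dosing falls under the rule after the one-time holds?**
- Substudy B: 200 − 20 sentinel participants = 180; 180/200 = 90%.
- Substudy A, combination group: 125 − 10 = 115; 115/125 = 92%. This is an upper figure, because the review needs at least 10 recipients.
- Pace, assuming even enrollment over the stated periods (about 1 month for Substudy B, 2 months for Substudy A): 200/30 = 6.7 vaccinations per day in Substudy B; 250/60 = 4.2 first vaccinations per day in Substudy A, where the pause covers Vaccination 1 only.

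No event rate is assumed. The available evidence points to a rare event: no related SAEs in Study C3671001 (Section 2.2.3.1) and a low incidence of severe or serious events for RSVpreF (Section 2.3.1).

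**The case against.** The strongest reply is that the narrow reading is plainly intended. The plural opening, together with repeated references to a stopping rule being met, suggests several rules, any one of which triggers the pause; a note for the whole list would then use the plural. The singular pause sentence can be read as meaning whichever rule has just been met. On this view the note has one job: to stop a solicited event being counted as unsolicited because it was entered on the AE CRF. The SAE part of the fifth criterion needs no such help. The SAP's retention of serious reactogenicity points the same way. Most list numbering is missing from the text available here, so any indentation under item 6 may also be lost, and the IRC charter, which is not among the documents, may settle the matter.

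It can also be said that the event would not go unseen. The sponsor is told of a confirmed Grade 4 reaction immediately and has staff unblinded for real-time review (Sections 10.9.8.2.3 and 10.10.8.2.3). The IRC reviews safety data from at least 1 week after vaccination (Sections 10.9.6.1 and 10.10.6.1). Finally, the dosing counts would be the same under perfect wording.

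Most of this stands. The narrow reading is the likelier intent, the event would be visible, and the counts describe exposure rather than the defect. But visibility is not a required pause, and no text in either document exempts serious events from the note.

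**Conclusion.** The concern holds, at minor severity. For a related serious solicited reaction within 7 days, the fifth criterion and a broad reading of the note lead to opposite actions, and neither document decides between them. The finding does not rest on the broad reading being intended; it needs only that the wording allows it.

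The practical effect is probably small, because the triggering event looks rare and other routes would bring it to the sponsor's attention. The effect cannot be quantified as a probability from the documents. The 90% and 92% figures, and the daily pace, show only how much dosing depends on this rule once the early holds are past. Confidence is medium, because the IRC charter or the original page layout could settle the scope.

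**What to change.** In Protocol Sections 10.9.10.5.1 and 10.10.10.5.1, state that the exclusion applies only to criterion 6 and to the Grade 4 unsolicited-AE part of the fifth criterion. Add that any death or related SAE still pauses randomization and dosing, once the sponsor confirms the rule is met, even if it began as a local reaction, systemic event or fever within 7 days. In Substudy A the pause would remain limited to Vaccination 1. Use matching wording in the IRC charter.

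The cost is one sentence in each section plus the charter text. If the narrow reading was intended, conduct does not change. The downside is a rare extra pause with IRC review.
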